5. ADVERSE EVENTS

There are no active interventions to the patients during the conduction of this study

Therefore there is no potential for any adverse events to the patients associated with the conduction of the study

The conduction of the study will not have any effect on the clinical decision-making by the responsible clinicians for the participants and it will not have any effect on the treatment of the participants.

What is analysed during the study is the recorded Somatosensory Evoked Potentials. Apart from the N20 Somatosensory Evoked Potential that is analysed during that clinical test we will further analyse the recordings with regards to the presence or absence of P25/30 Somatosensory Evoked Potentials. The Physicians responsible for the treatment of the patient will not become aware about the presence or absence of P25/30 SSEPs at any point of patient's care. The care physicians will continue to become aware about the results of N20 SSEP as currently.

The neurophysiology scientists who will interpret the recordings will not become aware about the patients' clinical data at any point of the study.

6. ASSESSMENT AND FOLLOW-UP

After the SSEP recording has been conducted, between 24 and 36 hours post ROSC, the patients will be followed up by members of the study team. Those members of the team will assess the patients, by CPC and by performing full neurologic clinical examination, on the day of ICU discharge and on the day of their discharge from Derriford Hospital. The online system SALUS of Derriford hospital will be used to follow up the patients after their discharge from ICU and before their discharge from the hospital. Through SALUS system, the members of the study team responsible for the patients follow up will be notified for the planned patients' discharge date in order the patients to be assessed by a study team member before they leave the hospital. The neurologic outcome, assessed with the Cerebral Performance Category [see figure 1 on the Appendix], will be recorded on the day of Hospital discharge [within the last 24 hours before discharge].

If a study participant died on ICU as a result of severe brain dysfunction or after the decision of ICU Consultant to be withdrawn from invasive organ support due to extremely poor prognosis and futility of further continuation of treatment, then, the discharge CPC would be the most recently recorded, after the patient have remained consistently off sedation [for a period of time varied for different sedatives or combination of sedatives].

Specifically, in a case that the ICU Consultant in charge considered withdrawing the invasive organ support in one of the study participants due to extremely poor prognosis, then the ICU consultant should notify the ICU research nurse in order one member of the team to perform the CPC score recording. The assessment by CPC must always take place before the decision for withdrawal of treatment is implemented and strictly before the palliative pathway is initiated. If the study team members failed to be notified by the ICU consultant about the withdrawal of treatment and the Palliative pathway is initiated before patient's CPC and neurologic examination recorded then the patient will be excluded from the study.

If a participant died unexpectedly from another cause rather than severe brain dysfunction and / or withdrawal of invasive organ support, then the most recent CPC before death [if possible to be recorded] will be based on the last available clinical assessment off sedation and will be considered as

indicative of neurologic outcome for the patients. In case the CPC could not be assessed, the patient would be excluded from the study analysis.

If patients die on ICU while still on sedation and before being possible to assess their CPC then they will be excluded from the study analysis as the assessment of their outcome based on CPC will not be possible.

The end of the study for each of the patients-participants will be either the discharge from hospital or their death at any time after the SSEP recording.

7. STATISTICS AND DATA ANALYSIS

7.1 DESCRIPTION OF STATISTICAL METHODS

Demographic information of participants will be summarized using descriptive statistics and presented in tables to provide an exploratory overview of the study population.

Continuous measures will be summarised as means, standard deviations and ranges where the distribution appears normal, and as medians, inter-quartile ranges and ranges otherwise.

Categorical data will be summarised by frequencies and percentages.

The primary outcome measure is the CPC score at hospital discharge with discrete values ranging from 1 to 5. The score will be dichotomised as 1-2 (positive or good outcome) and 3-5 (negative or poor outcome).

Sensitivity, specificity and predictive values of P25/30 in predicting poor outcome will be computed and the results compared to that of N20. Where appropriate, parameter estimates will be presented with 95% confidence intervals. Significant demographic and clinical predictors of poor neurological outcomes will be assessed and identified using regression models.

Statistical data analysis will be undertaken once data collection from the required number of participants is completed. No interim analysis is scheduled for this study.

Analyses will be performed in SPSS version 24 (or later), supplemented where required by Stata SE version 14.2 (or later) and R.

a. THE NUMBER OF PARTICIPANTS

Sample size calculation was based on diagnostic test accuracy (adequate sensitivity) of P25/30. A previous study (Kim et al. 2018) on patients treated by hypothermic targeted temperature management showed that the sensitivity of P25/30 in predicting poor outcome is 90.12% (95% CI, 81.5–95.6%). Though the proposed study will be based on those who are not treated by hypothermic targeted temperature management, the result (90%) is the 'best' available information regarding pre-determined sensitivity of P25/30. From experience of the team and analysis of the past three-years

pilot data, the prevalence of poor outcome was assumed to be 75%. In order the maximum marginal error of estimate does not exceed from 5% with 95% confidence level, and adjusting for drop-out/lack of consent at 3%, the minimum required sample size will be 115. No power was assumed in the calculation of the sample size as there is no testing of hypothesis.

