1.1 BACKGROUND

Suffering an Out of Hospital Cardiac Arrest (OHCA) is a global health problem with a yearly incidence of approximately 1:1000 people worldwide (1). In-hospital-cardiac-arrests (IHCA) affect 1-1.5 per 1000 in-patients (2). Internationally, recent survival figures for such events are 26% and 22% respectively (3,4). Much of this mortality is due to patients suffer devastating neurological damage, and so go on to receive palliative care. Locally, 200 patients were admitted to the Derriford General Intensive care in the last 3 years following an OHCA. Of those, patients who reach the intensive care, 70% died (2). Many patients who do not die will suffer varying degrees of neurological damage. Neurological outcome is most commonly measured using the Cerebral Performance Categories [CPC] [appendix figure 1] either at ICU or hospital discharge or at 3-6 months post cardiac arrest.

Up to 20% of patients suffering a cardiac arrest will still be in a coma at one week post Return Of Spontaneous Circulation [ROSC]. Some of these patients will make a good recovery (5). Predicting devastating irreversible neurological damage often takes time and requires a multimodal approach using clinical testing, electrophysiological tests, blood biomarkers, and radiological imaging. In the most recent guidelines issued by the Resuscitation Council UK in 2015 a specific prognostication algorithm is provided to facilitate the integration of these clinical signs and investigations in available in order to achieve the best possible prognostic accuracy [Figure 1].

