Importantly, early and accurate detection of patients with severe cerebral damage prevents unnecessary patient suffering and assists with clear communication with relatives, reducing their distress. There are a number of known factors that are associated with a poor outcome: Age, non-witnessed arrest, lack of bystander cardiopulmonary resuscitation [CPR], presence of a non-shockable rhythm [Asystole or Pulseless Electrical Activity (PEA)], Anoxia time [time lapsed from cardiac arrest until ROSC], requirement for adrenaline, a low pH and PaCO₂ on admission (6). None of these prognostic markers have sufficient sensitivity or specificity to make accurate prognostic decisions. Many of the clinical signs [pupils' reactivity to light, Glasgow Coma Scale (GCS), reflexes, presence of myoclonus] and laboratory / radiological tests [Computerised Tomography (CT) scans, Electroencephalogram (EEG), Neuron Specific Enolase (NSE), Magnetic Resonance Imaging (MRI) scan] also suffer similar uncertainty – either when used alone or in combination in the context of a multimodal approach – especially early in an admission. One exception is the Short-latency Somatosensory Evoked Potentials (SSEPs). During this test, specific electrical signals are recorded in specific area of the brain [cortex]. These electrical signals are produced after stimulation of a nerve on the hand. This test establishes presence or absence of intact brain electrical activity. At 20 milliseconds after median nerve stimulation, a response, an electrical signal, should be recorded in the corresponding area of the brain which is called sensory cortex. This electrical signal is called N20. Total absence of N20s is strongly correlated with a poor outcome.

Figure 1: Resuscitation Council UK Post cardiac arrest prognostication algorithm

(1) At ≥ 24 h after ROSC in patients not treated with targeted temperature
 (2) See text for details.

However, the presence of N20s does not equate with a good outcome. Many patients with unilaterally or bilaterally present N20s may still have devastating neurological damage.

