3.1 STUDY OUTCOME MEASURES

Primary Endpoint: Neurologic outcome assessed by Cerebral Performance Category [CPC] score at hospital discharge.

Secondary endpoints: Mortality at hospital discharge and at 28 days [which occurs first], comparison of prognostic benefit of N20 and P25/30 SSEPs-based multimodal prognostic models.

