4. PARTICIPANT ENTRY

4.1 RECRUITMENT AND CONDUCTION OF THE STUDY

The general management of adult comatose survivors after OHCA, who are admitted to the Derriford ICU, consists of provision of organ support as required [mechanical ventilation, cardiovascular support, renal replacement therapy], targeted temperature management aiming to maintain patients in normothermic condition for the first 72 hours, continuous invasive and non-invasive multimodal monitoring [vital signs, respiratory and haemodynamic monitoring, neurologic monitoring] and treatment of the underlying cause of cardiac arrest [if known-diagnosed]. The patients remain sedated for the first 36 hours to facilitate brain protection, optimisation of patient's organ function parameters and achievement of targeted temperature within very strict temperature limits [For the first 24 hours temperature target is 36°C and for the next 48 hours the temperature target is 36-37°C]. The targeted temperature management is achieved with the use of external cooling devices. The neurologic prognostication of the post cardiac arrest patients is mainly based on a multimodal approach guided by the clinical picture of the patient [Level of consciousness, Glasgow Coma Scale, presence or absence of reflexes and focal neurologic signs], the results of the CT imaging studies [CT or MRI of the Head], the results of the Electroencephalogram and SomatoSensory Evoked Potentials [SSEPs] recording which usually are performed after the first 24 hours post ROSC. The SSEPs recording are performed in all comatose survivors after OHCA who are admitted to Derriford ICU as an integral part of their normal care. The recording and the analysis of the recording are conducted by the members of the neurophysiology team in Derriford Hospital. The main aim of that routine, established and used for the last 3 years, prognostication test is to assess the presence or absence of the N20 SSEP in comatose survivors after out of hospital cardiac arrest. According to the international medical literature and the national guidelines, N20 presence is associated with unknown [ranging from full neurological recovery to severely disabled status] neurological prognosis, whereas N20 absence is always reliably associated with poor neurologic prognosis.

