7.3 THE LEVEL OF STATISTICAL SIGNIFICANCE

Whenever applicable, a 5% level of significance will be used.

7.4 CRITERIA FOR THE TERMINATION OF THE TRIAL.

As this is not an interventional study, the chance to terminate the trial is minimal.

7.5 PROCEDURE FOR ACCOUNTING FOR MISSING, UNUSED, AND SPURIOUS DATA.

Spurious and/or missing data will be summarised and reasons for missingness given where possible. All data analyses will be based on the complete data only.

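### Selecting predictors by significance with about 28 good outcomes invites chance predictors and overstates AUC unequally in the N20 and P25/30 models

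*Combined protocol and SAP*

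**What the plan says.** Section 7.1 of the combined protocol and SAP dichotomises CPC at hospital discharge (1–2 good, 3–5 poor) and plans accuracy measures for P25/30 and N20. On modelling it has one sentence: "Significant demographic and clinical predictors of poor neurological outcomes will be assessed and identified using regression models". Section 7.3 adds "Whenever applicable, a 5% level of significance will be used", and Section 7.5 adds "All data analyses will be based on the complete data only".

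Section 3.1 lists as a secondary endpoint the "comparison of prognostic benefit of N20 and P25/30 SSEPs-based multimodal prognostic models". No section says how these models are built, whether they share covariates and patients, or how they are compared.

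The document names no covariate set, limit on parameters, selection rule, performance measure or internal validation. Section 1.1 says "There are a number of known factors that are associated with a poor outcome" and lists eight of them. Section 4.1 has a longer list of data to collect. Neither list is designated as the model covariates. Section 7.6 makes a separate SAP optional and does not require it to settle these matters.

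**The concern.** Read plainly, identifying significant predictors at a 5% level means keeping those with p<0.05. In a small data set this retains some variables by chance, and the model then looks better in the data that chose it than in new patients. The size of that optimism depends on how much of the model rests on selected covariates, so it need not be equal for two models that are to be compared.

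At stake are the list of reported predictors and the secondary comparison of the N20 and P25/30 models. If covariates are also chosen separately beside each marker, a difference in performance cannot be credited to the marker alone. Complete-case analysis could then place the two models in different patients as well.

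**Working it through.** **The plan's sample size.** Inputs from Section 7(a): sensitivity 90%, margin 5%, 95% confidence, poor-outcome prevalence 75%, loss 3%. The usual formula gives 1.96² × 0.90 × 0.10 / 0.05² = 138.3 poor outcomes; 138.3 / 0.75 = 184.4 patients; 184.4 / 0.97 = 190.1. The stated 115 does not reproduce. That is a separate matter: only the cohort size is needed here, and 115 is taken as stated.

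**Good outcomes (the smaller group).**
- 115 × 0.97 × 0.25 = 27.9
- Prevalence of poor outcome 80%: 115 × 0.97 × 0.20 = 22.3; 70%: 115 × 0.97 × 0.30 = 33.5
- With the 120 patients of Section 3: 120 × 0.97 × 0.25 = 29.1

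**Candidates.** Seven of the eight factors in Section 1.1 are on the Section 4.1 data list. Adrenaline is not, and pH and PaCO₂ are recorded as 24-hour means. I take 7–10 candidates as the working range, which leaves 28/7 = 4.0 to 28/10 = 2.8 good outcomes per candidate.

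**Chance predictors.** For k independent null candidates the chance of at least one p<0.05 is 1 − 0.95^k: 0.302 for k = 7 and 0.401 for k = 10. Simulation with 84 poor and 28 good outcomes (univariable screening and backward elimination) gave 28–29% and 39–40%. With equal correlation of 0.3 to 0.5 (assumed) among 10 candidates, screening gave 36% to 30%.

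**Optimism, covariates only.** The plan names no performance measure; AUC is used here. Three candidates are real, with shifts of 0.4 or 0.6 SD (assumed). Apparent and new-data AUC, with the gap:

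| Method | 0.4 SD | 0.6 SD |
|---|---|---|
| Backward, 7 candidates | 0.678 − 0.604 = 0.074 | 0.773 − 0.720 = 0.053 |
| Backward, 10 candidates | 0.688 − 0.601 = 0.087 | 0.781 − 0.714 = 0.067 |
| Screening, 7 candidates | 0.676 − 0.605 = 0.071 | 0.773 − 0.727 = 0.046 |
| Screening, 10 candidates | 0.683 − 0.603 = 0.080 | 0.780 − 0.723 = 0.057 |
| Three pre-specified | 0.706 − 0.669 = 0.037 | 0.780 − 0.756 = 0.024 |

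With 22 or 34 good outcomes and 7–10 candidates, the gap under selection is 0.04–0.09.

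**Optimism with the marker in the model.** Sensitivity 90% for P25/30 is the plan's figure; 60% for N20 and specificity 98% for both are assumed. With 7 or 10 candidates, backward selection at p<0.05 and the marker forced in:

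| | N20 model | P25/30 model |
|---|---|---|
| Gap, covariates selected | 0.034–0.041 | 0.012–0.016 |
| Gap, three pre-specified covariates | 0.016–0.022 | 0.009–0.013 |

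With selection, the apparent P25/30-minus-N20 difference was 0.060–0.097 and the new-data difference 0.084–0.121. The apparent value is too small by 0.084 − 0.060 = 0.024 at both ends of these ranges, and by about 0.02–0.03 overall. Its run-to-run SD was 0.045–0.067.

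**Different covariates.** Separate selection beside each marker gave different covariate sets in about 70–90% of runs (55% with 7 candidates if both markers have sensitivity 60%).

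**Separation.** Section 1.1 reports that in the cited retrospective study of 116 patients every patient with absent P25/30 had a poor outcome. Section 4.1 states that "N20 absence is always reliably associated with poor neurologic prognosis". The cited sensitivity of 90.12% (81.5–95.6%) matches 73/81, so 116 − 81 = 35 good outcomes had no false positive. The exact lower 95% limit for specificity is 0.025^(1/35) = 0.900. The chance that none of 28 good-outcome patients has an absent marker is 0.90^28 = 0.05, 0.95^28 = 0.24 or 0.99^28 = 0.75. As a prediction from 35/35 it is 36/64 = 0.56 (uniform prior) or 0.75 (Jeffreys prior). In that event ordinary logistic regression gives no finite marker coefficient and no valid Wald interval.

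**The case against.** The strongest reply is that the gap in the plan is real but its consequences are modest. Most of that stands.

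- **The covariate-only gaps are not those of the marker models.** Correct. With a strong marker in the model the overstatement falls to 0.03–0.04 and 0.01–0.02.
- **A reader might infer that the comparison would flatter P25/30.** The calculation does not support this. The weaker model carries more optimism, so under the assumed sensitivities the advantage of P25/30 is understated, by less than one run-to-run SD.
- **A reader might infer that a p<0.05 rule would discard a separated marker.** The documents do not support this. Section 7.1 applies significance to demographic and clinical predictors, and the models in Section 3.1 are by definition based on each marker. Separation also presumes absent/present coding, whereas Section 4.1 additionally plans amplitudes and their ratio.
- **A reader might count every collected variable as a candidate.** That would give far higher false-predictor rates, but it treats related measures such as pH, base excess and lactate as independent. It also counts items available only in some patients, such as the CT report and ammonia.
- **The all-null case is a benchmark.** Section 1.1 regards several candidates as established factors. The runs with three real predictors address this, and optimism remains.
- **Two links are inferred:** that the Section 7.1 sentence governs the Section 3.1 comparison, and that covariates would be selected separately for each marker. One shared selection would give identical covariate sets. If the first link is rejected, the endpoint has no modelling method at all.
- **A SAP may follow.** Section 7.6 permits one but does not require it.

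**Conclusion.** The point holds at moderate size. With about 28 good outcomes (22–34 for prevalence 80–70%), keeping predictors at p<0.05 gives at least one false predictor in about 28–40% of studies with 7–10 independent null candidates. It overstates AUC by about 0.05–0.09 without a marker, 0.03–0.04 with N20 and 0.01–0.02 with P25/30. The apparent difference between the marker models is therefore biased, and understated by about 0.02–0.03.

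The AUC sizes rest on the assumed predictor strengths, N20 sensitivity of 60% and specificity of 98%. The direction of the bias in the difference depends on P25/30 being the more sensitive marker. The separation risk carries over a study that recorded SSEPs at 3–4 days under hypothermic management, which is an assumption for this cohort.

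A reader might extend the concern to the main results. That is not supported: sensitivity, specificity and predictive values do not use the regression. The harm is confined to the predictor analysis and one secondary endpoint.

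**What to change.** Before the databanks are merged, replace the regression sentence in Section 7.1 with text such as:

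> Two logistic models for poor outcome (CPC 3–5) will be fitted in the same patients with the same two or three covariates, named here in advance. Model A adds the N20 result and Model B the P25/30 result, each coded as in the accuracy analysis. Both will be fitted by Firth or an equivalent penalised likelihood. The bootstrap optimism-corrected AUC of each model, and their corrected difference with a bootstrap 95% confidence interval, will be reported. Other demographic and clinical predictors will be reported as exploratory, with none selected by p-value.

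The study team should choose the covariates from the Section 1.1 factors that are collected for all patients.

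A limited check (60 runs, 60 resamples each, covariate shifts of 0.5 SD, three covariates) gave these AUCs:

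| | Apparent | Corrected | New data |
|---|---|---|---|
| Sensitivity 60% | 0.891 | 0.872 | 0.873 |
| Sensitivity 90% | 0.970 | 0.961 | 0.962 |
| Model difference | 0.078 | 0.088 | 0.089 |

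Coverage of the interval for the difference was not checked, so the statistician should name the bootstrap form to be used.

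The cost is a paragraph of text and some extra analysis in R or Stata, both already named in Section 7.1. The models are narrower than the protocol's own account of prognostication, which "requires a multimodal approach using clinical testing, electrophysiological tests, blood biomarkers, and radiological imaging", and should be described accordingly. No confirmatory claims can be made about other predictors. Three covariates plus a marker leave 28/4 = 7 good outcomes per parameter (22/4 = 5.5 to 34/4 = 8.5), so optimism correction is still needed.

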3. STUDY DESIGN

Prospective Observational, Non-interventional, Study: Analysis of the recordings of Somatosensory Evoked Potentials test which is performed for prognostication in Derriford intensive Care Unit, in comatose survivors after Out of Hospital Cardiac Arrest. The interpretation of the recordings will include the presence or absence of P25/30 SSEPs, of N20 SSEP and possible other short or long latency evoked potentials on these recordings. After the interpretation of the recordings then a test for possible correlations of the recorded P25/30 SSEPs with the neurologic prognosis of the survivors will be performed.

Estimated Study Duration: 24-36 months

Estimated Number of patients: One hundred and twenty adult Intensive Care Unit patients. In order to be included in the study, all patients must be adults, comatose survivors after out of hospital cardiac arrest who are admitted to Derriford Intensive Care Unit.

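### The planned 115 patients give about ±6.4 points on sensitivity, not the stated ±5; the plan's own inputs call for about 190

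*Combined protocol and SAP*

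**What the plan says.** Section 7.1a identifies the target quantity: "Sample size calculation was based on diagnostic test accuracy (adequate sensitivity) of P25/30". It gives four inputs.

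- **Sensitivity.** An earlier study of patients treated with hypothermic temperature management "showed that the sensitivity of P25/30 in predicting poor outcome is 90.12" per cent, with a 95% interval of 81.5–95.6%. The plan adopts the rounded value: "the result (90%) is the 'best' available information regarding pre-determined sensitivity of P25/30".
- **Prevalence.** From team experience and three years of pilot data, "the prevalence of poor outcome was assumed to be 75" per cent.
- **Precision.** The target is that "the maximum marginal error of estimate does not exceed from 5% with 95% confidence level".
- **Loss.** The section concludes: "adjusting for drop-out/lack of consent at 3%, the minimum required sample size will be 115".

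No formula is given, and the section says that power was not considered because no hypothesis is tested. Section 3 gives a different enrolment figure: "One hundred and twenty adult Intensive Care Unit patients".

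**The concern.** A patient contributes to the sensitivity estimate only if the outcome is poor (CPC 3–5). The number of poor-outcome patients, not the number enrolled, therefore sets the precision. At 90% sensitivity a 5-point margin needs more poor-outcome patients than the plan enrols in total, so 115 looks too small before prevalence or loss is considered.

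Sensitivity is named in the second primary objective (Section 2), and the margin is the only quantitative justification for the study's size. If it is wrong, an ethics committee or a later reader is told of a precision that the design does not have under its own assumptions.

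**Working it through.** **Inputs (all from Section 7.1a unless noted).** Sensitivity Se = 0.90 (0.9012 unrounded); prevalence of poor outcome = 0.75; margin d = 0.05; two-sided 95% confidence, z = 1.96; loss = 3%; stated size 115. Section 3 gives 120.

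**Attempt to reproduce 115.** The standard precision formula is

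n(poor) = z² × Se × (1 − Se) / d², then N = n(poor) / prevalence / (1 − loss).

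- n(poor) = 1.96² × 0.90 × 0.10 / 0.05² = 138.3
- 138.3 / 0.75 = 184.4
- 184.4 / 0.97 = 190.1, or 191 if each step is rounded up

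With Se = 0.9012 the steps are 136.8, 182.4 and 188.1 (189 rounded up). The stated 115 is not reproduced; it is about 40% short (1 − 115/190.1 = 0.395).

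**Other conventions, all with a 5-point margin.**

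| Variant | N after 3% loss |
|---|---|
| Prevalence ignored | 142–144 |
| Multiplied by prevalence instead of divided | 107–108 |
| One-sided 95% | 133–135 |
| One-sided 95%, prevalence ignored | 100–102 |
| 1 − prevalence used | 565–572 |
| Wilson interval | 194 |
| Clopper-Pearson interval | about 218 |

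None gives 115. Relaxing the margin to 6.5 points does come close: 1.96² × 0.09 / 0.065² = 81.8; / 0.75 / 0.97 = 112.5.

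**What the planned numbers deliver at Se = 0.90.** Half-width = 1.96 × √(0.09 / n(poor)).

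| Enrolled | Loss | Poor-outcome patients | Half-width |
|---|---|---|---|
| 115 | 3% | 115 × 0.97 × 0.75 = 83.7 | 6.4 points |
| 115 | none | 115 × 0.75 = 86.25 | 6.3 points |
| 120 | 3% | 120 × 0.97 × 0.75 = 87.3 | 6.3 points |
| 191 | 3% | 191 × 0.97 × 0.75 = 139.0 | 5.0 points |

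These are normal-approximation (Wald) figures. For 83.7 poor outcomes the Wilson half-width is 6.5 points. The exact (Clopper-Pearson) interval for 76 of 84 is 82.1–95.8%, a half-width of about 6.9. Even if all 115 patients were evaluable and all had a poor outcome, the Wald half-width would be 1.96 × √(0.09 / 115) = 5.5 points.

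**When would ±5 hold?** With 83.7 poor outcomes, Se × (1 − Se) must not exceed 83.7 × 0.05² / 1.96² = 0.0545, which requires a sensitivity of about 94.2% or more.

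**Cross-check against the plan's own source figure.** The quoted 90.12% (81.5–95.6%) matches 73/81 with a Clopper-Pearson interval. The count is inferred, since the protocol gives only the earlier study's total of 116 patients (Section 1.1). On that inference about 81 poor-outcome patients gave about ±7 points, and this study expects about 84.

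**The case against.** **A route to 115 exists.** Section 1.1 reports 200 local admissions in three years. A finite-population correction with that figure gives 138.3 / (1 + 137.3/200) = 82.0 poor-outcome patients, and 82.0 / 0.75 / 0.97 = 112.7. Rounding up at each step gives 83, 111 and 115, exactly the stated number. So 115 may come from an unstated method rather than a slip, and the sponsor should be asked for the formula. It does not rescue the claim. Section 7.1a mentions no such correction. It would also apply all 200 admissions to a count of poor-outcome patients; with 75% of 200, that is 150, the result is 138.3 / (1 + 137.3/150) / 0.75 / 0.97 = about 99. And it would describe precision for a closed group of 200, whereas the aim is to validate a prognostic marker for later patients.

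**The margin could still be met.** The 94.2% sensitivity that would give ±5 lies inside the source's interval. That is fair, and the accurate statement is that the margin is not met at the 90% the plan assumes.

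**The source interval is not a contradiction in the strict sense.** A wider interval in one study does not preclude a narrower target in another. The comparison is supporting evidence only.

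**115 and 120 can coexist.** One is called a minimum and the other an estimate. This is true, but neither gives 5 points.

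**The consequence is modest.** The study re-reads routine recordings, claims no power and plans to report confidence intervals where appropriate, so the actual precision should be visible at the end. The gap is about 1.4 points of half-width. That limits the harm, but the only stated basis for the sample size is still incorrect.

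**Conclusion.** The concern holds. On the plan's own inputs, a 5-point margin at 95% confidence needs about 190 patients (188 with the unrounded sensitivity) against 115 stated. With 115 enrolled, the half-width is about 6.4 points by the Wald method and about 6.9 by the exact method.

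The result assumes 90% sensitivity, 75% poor outcome and 3% loss, with the whole 3% treated as loss after enrolment. If part of it is refusal of consent before enrolment, the figure moves only towards 6.3.

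The actual precision could be worse. Sections 4.1, 4.5 and 6 also remove patients whose CPC cannot be assessed, those whose assessment before palliation was missed and those with uninterpretable recordings, and Section 7.5 restricts analysis to complete data. If these losses exceed 3%, the interval widens further. The error should be corrected before the sample-size statement is relied on.

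**What to change.** Rewrite the closing part of Section 7.1a along these lines:

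> *With 115 patients enrolled, about 112 are expected to be evaluable and about 84 to have a poor outcome. At a sensitivity of 90%, the 95% confidence interval would have a half-width of about 6.4 percentage points (normal approximation; about 6.9 by the Clopper-Pearson method).*

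If the target is the 120 of Section 3, the normal-approximation figure is about 6.3 points, from about 87 poor outcomes. In addition:

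- Delete the claim of a 5% margin.
- Use one target number in Sections 3 and 7.1a.
- State the formula. If a finite-population correction was used, say so and justify it, or drop it.
- Say that the figure is conditional on no more than 3% of enrolled patients being lost from the analysis for any reason.

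The cost is one paragraph of text and a slightly less favourable stated precision. No extra patients are needed for this correction. Keeping the 5-point margin instead would mean enrolling about 190 patients.
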